Subjects will undergo first CNS imaging evaluation at week 6 (\pm 3 days). Subsequently, subjects will be evaluated every 6 weeks (42 days \pm 3 days), independently of any treatment delays, with radiographic imaging to assess response to treatment, until week 30/Cycle 10. Subjects will then undergo imaging evaluation every 12 weeks (84 \pm 7 days). RECIST 1.1 will be used as the primary response rate efficacy endpoint. RECIST 1.1 will be adapted as described in Section 4. to adjust for the tumor response patterns seen with pembrolizumab treatment (e.g., tumor flare), and this adapted/modified RECIST 1.1 will be used by the sites for treatment decisions. The primary response rate efficacy endpoint will be based on independent central review using RECIST 1.1 [1]. Modified RECIST 1.1 will also be used by the local site to determine eligibility and make treatment decisions. MRI of the brain will be the primary radiological method of disease assessment using the RANO-BM criteria.

Subjects may submit an optional tumor tissue sample, if feasible, for biomarker analyses and PDL1 expression evaluation. Subjects with an inadequate archival sample may obtain a new biopsy and subjects with an inadequate newly obtained biopsy may undergo re-biopsy at the discretion of the investigator.

AEs will be monitored throughout the trial and graded in severity according to the guidelines outlined in the National Cancer Institute (NCI) Common Terminology Criteria for AEs (CTCAE) Version 4.03.

Treatment will continue as outlined in Table 1 until documented disease progression, unacceptable AEs, intercurrent illness that prevents further administration of treatment, investigator's decision to withdraw the subject, subject withdraws consent, pregnancy of the subject, noncompliance with trial treatment or procedure requirements, completion of 24 months of treatment with pembrolizumab, or administrative reasons.

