4.4.6 Response Assessment

MRI of the brain will be the primary radiological method of disease assessment using RECIST 1.1 and the RANO-BM criteria (See Appendix 1). Quantitative imaging changes on multiparametric MRI will be captured to determine early biomarkers of immune response. Standard of care brain MRI with intravenous gadolinium contrast and contrast enhanced CT chest/abdomen/pelvis or PET-CT, as clinically indicated, will be used to assess both intracranial and extracranial disease at Screening and every 6 weeks after the start of treatment up to cycle 9. Imaging may occur up to 72 hours prior to scheduled cycle. Screening MRI and CT assessments must occur within 28 days prior to day 1.

If an MRI, CT chest/abdomen/pelvis or PET-CT is not already performed as standard of care per Schedule of Assessments in Section 5, the investigator may choose to perform either or both procedures for assessing the progress of the patient.

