Appendix 2: RECIST v1.1

Response Evaluation Criteria in Solid Tumors (RECIST v1.1 Criteria)

The RECIST criteria should be used to assess response to treatment. Only patients with measurable disease should be entered in the study. Measurable extracranial disease is defined as the presence of one lesion that can be accurately measured in at least one dimension (longest diameter to be recorded) as ≥ 2.0 cm with conventional techniques (or as ≥ 1.0 cm by spiral CT). Evaluable lesions should be followed for the assessment of response. Non-measurable lesions include bone lesions, ascites, pleural/pericardial effusion, lymphangitic carcinomatosis, abdominal masses that are not confirmed by CT, and cystic lesions. Disease progression and response evaluations for intracranial and extracranial disease will be determined according to the definitions established in the Response Evaluation Criteria in Solid Tumours (RECIST v1.1). Minor modifications will be applied to the assessment of intracranial lesions:

- General: target lesions should be representative of the subject's baseline tumor burden and should be selected based on their size (i.e. lesions with the longest diameter) and their suitability for accurate repeat assessment.
- Intracranial lesions: (the modifications to RECIST v1.1. impact the number and the minimal size of the target lesions selected at baseline) up to five lesions should be selected as target lesions; all brain lesions in excess of these five target lesions have to be regarded as non-target lesions. Measurable lesions are defined as those that can be accurately measured in at least one dimension with the longest diameter ≥ 5 mm when evaluated with contrast-enhanced MRI. Contrast-enhanced MRI is the only imaging modality accepted for assessment of intracranial lesions.
- Extracranial lesions: up to two lesions per organ representative of all involved organs should be selected as target lesions; the total number of target lesions should not exceed five and all lesions in excess of these five target lesions have to be regarded as non-target lesions.

Baseline Documentation of Intracranial Target and Non-Target Lesions

- All baseline lesion assessments must be performed within 28 days of the first dose of study treatment.

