- Bone scans, FDG-PET scans or X-rays are not considered adequate imaging techniques to measure bone lesions.
- All other lesions (or sites of disease, excluding the brain) should be identified as non-target and should also be recorded at baseline.
- Non-target lesions will be grouped by organ. Measurements of these lesions are not required, but the presence or absence of each should be noted throughout follow-up.

Overall Intracranial Response - Evaluation of Intracranial Target Lesions

Definitions for assessment of response for intracranial target lesion(s) are as follows:

- Complete Response (CR): Disappearance of all target lesions.
- Partial Response (PR): At least a 30% decrease in the sum of the diameters of target lesions, taking as a reference, the baseline sum of the diameters (e.g. percent change

Proprietary Information of MD Anderson

from baseline).

- Stable Disease (SD): Neither sufficient shrinkage to qualify for PR nor sufficient increase to qualify for progressive disease.
- Progressive Disease (PD): At least a 20% increase in the sum of the diameters of target lesions, taking as a reference, the smallest sum of diameters recorded since the treatment started (e.g. percent change from nadir, where nadir is defined as the smallest sum of diameters recorded since treatment start). In addition, the sum must have an absolute increase from nadir of 5mm.
- Not Evaluable (NE): Cannot be classified by one of the four preceding definitions.

Note: If an intracranial target lesion disappears and reappears at a subsequent time point it should continue to be measured. The response at the time when the lesion reappears will depend upon the status of the other lesions. For example, if the disease had reached a CR status then PD would be documented at the time of reappearance. However, if the response status was PR or SD, the diameter of the reappearing lesion should be added to the remaining diameters and response determined based on percent change from baseline and percent change from nadir.
- Patients, who in the opinion of the treating physician investigator have had a substantial decline in their performance status and have clinical evidence of progressive disease may be classified as having progressive disease.

Proprietary Information of MD Anderson

Appendix 3: Current National Cancer Institute Common Terminology Criteria for Adverse Events (NCI CTCAE Version 4.03)

Please use the following link to the NCI CTCAE website:

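### Read literally, Appendix 2 leaves the baseline sum out of the reference for target-lesion progression, so that rule cannot be met at week 6 and some patients can be scored as SD > 6 months

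*Combined protocol and SAP*

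**What the plan says.** The primary endpoint is CBR in the brain: CR, PR, or SD lasting more than 6 months, by modified RECIST 1.1 (Sections 2.1 and 6.1). The intracranial response definitions are in Appendix 2.

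- **PD** needs at least a 20% increase over the reference sum. The reference is described twice as dating from the start of treatment; the second time, "nadir is defined as the smallest sum of diameters recorded since treatment start". There is also a size condition: "In addition, the sum must have an absolute increase from nadir of 5mm".
- **PR**, in the same list, is measured from the baseline sum.
- **SD** is what is left over: "Neither sufficient shrinkage to qualify for PR nor sufficient increase to qualify for progressive disease".
- **Baseline timing.** Appendix 2: "All baseline lesion assessments must be performed within 28 days of the first dose of study treatment". Section 4.4.6: "Screening MRI and CT assessments must occur within 28 days prior to day 1".
- **First on-treatment scan.** Section 3: "Subjects will undergo first CNS imaging evaluation at week 6".
- **Declared modifications.** Appendix 2 adopts the RECIST v1.1 definitions for progression and response and says that "the modifications to RECIST v1.1. impact the number and the minimal size of the target lesions selected at baseline". A changed reference for PD is not among them.

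**The concern.** The baseline sum normally predates treatment, so a nadir restricted to sums since treatment start does not contain it. At week 6 only one qualifying sum exists, the week-6 sum itself. The increase over nadir is then zero whatever happened since baseline, and the patient falls into SD unless the sum meets PR or CR. Later growth is judged from a week-6 sum that may already be enlarged.

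SD > 6 months counts as benefit, so a late or missed PD can turn a non-benefit into a benefit. The direction is one-sided: leaving baseline out can only delay PD or remove it. With 25 patients in Cohort A, each misclassified patient moves CBR by 4 points. PFS dates would also move later if PFS uses the same rule.

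**Working it through.** **The plan's own figure.** From Section 6.1: n = 25, control rate p0 = 0.16, anticipated rate p1 = 0.35, one-sided alpha 0.10.

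Power = Φ{[(p1 − p0)√n − z₀.₉₀√(p0(1 − p0))] / √(p1(1 − p1))} = Φ{[0.95 − 1.2816 × 0.3666] / 0.4770} = Φ(1.007) = 0.843. This reproduces the stated 84%.

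The test implies a cut at 25 × 0.16 + 1.2816 × √(25 × 0.16 × 0.84) = 6.35, so 7 or more of 25. Exactly, that rule has alpha 0.092 and power 0.827. Nothing here depends on the PD definition.

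**The PD rule applied both ways.** PD requires an increase of at least 20% and at least 5 mm over the reference. The sums are illustrative assumptions in mm, read at baseline and then every 6 weeks.

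| Sums | First PD, baseline in reference | First PD, literal wording |
|---|---|---|
| 20, 28, then flat | week 6 (+8, +40%) | never; SD throughout |
| 20, 30, 45, 67 | week 6 (+10, +50%) | week 12 (45 v 30: +15, +50%) |
| 20, 22, 30 | week 12 (+10, +50%) | week 12 (30 v 22: +8, +36%) |
| 20, 12, 10, 16 | week 18 (16 v 10: +6, +60%) | week 18 (same) |
| 20, +3 per scan | week 12 (26: +6, +30%) | week 18 (29 v 23: +6, +26%) |
| 20, +2 per scan | week 18 (26: +6, +30%) | week 24 (28 v 22: +6, +27%) |
| 20, +1.5 per scan | week 24 (26: +6, +30%) | week 30 (27.5 v 21.5: +6, +28%) |
| 30, +2 per scan | week 18 (36: +6, +20%) | week 30 (40 v 32: +8, +25%) |
| 40, +2 per scan | week 24 (48: +8, +20%) | week 36 (52 v 42: +10, +24%) |

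**Who can enter CBR.** Six months is about 26 weeks. Two groups can cross that line because of the wording alone.

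- *Early growth, then plateau.* The first row stays SD indefinitely.
- *Some slow growers.* With PD at week 30, SD exceeds 6 months if its duration runs to the PD date, but not if it runs to the last SD scan (week 24). The plan does not say which. In the 40 mm row the last SD scan is week 30, so that patient counts either way. If scans become 12-weekly after week 30, as Section 3 states, PD there is found at week 42 (54 v 42: +12, +29%).

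**What misclassification would do.** The documents do not give the share of such patients. Assume that 4, 8 or 12 percentage points (1, 2 or 3 patients of 25) are added to a true CBR of 16%. The binomial probability of 7 or more of 25 is then:

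| CBR as scored | P(≥ 7 of 25) |
|---|---|
| 16% | 0.092 |
| 20% | 0.220 |
| 24% | 0.393 |
| 28% | 0.575 |

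**The case against.** The strongest reply is that nobody would score it this way. Appendix 2 adopts RECIST v1.1 and limits its changes to lesion number and size. Sections 2.3 and 4.2.4 speak of sums running from baseline onwards. A reader with only a baseline and a week-6 scan would naturally compare the two. This makes loose drafting the likelier explanation, but it does not repair the printed definition. PR and PD are given different references in one list, so someone coding the rule has textual grounds to leave baseline out.

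A reader might infer that growth by week 6 can never be PD. The documents do not support that. Sections 3 and 4.4.6 also apply RANO-BM to brain MRI. Appendix 1 lists a 20% increase with no reference sum named, non-target progression, new lesions and substantial clinical decline. Appendix 2 separately allows PD on clinical evidence with a decline in performance status. These routes stand, but they do not close the gap. Appendix 1 is silent on the reference, its iRANO note qualifies the new-lesion route in the first six months, and the clinical route misses symptom-free radiographic growth.

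A reader might also infer that every steady progression is dated late. It is not: 20, 22, 30 mm is PD at week 12 either way. Nor is SD at week 6 itself benefit; fast growers become PD at the next scan, well short of six months.

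Two further points stand. Section 3 assigns the primary response endpoint to central review by RECIST 1.1, while Sections 2.1 and 6.1 say modified RECIST 1.1, so it is not settled that this sentence alone decides CBR. And the documents do not say how the 16% control was scored; if the same convention was used there, the comparison would be less biased.

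**Conclusion.** The concern holds as a defect in a printed rule that can feed the primary endpoint. Taken literally, the Appendix 2 target-lesion criterion cannot be met at week 6. Patients with early growth and then a plateau, and some slow growers, can be scored SD > 6 months. Some PFS dates move later if the same rule is applied. The direction is towards benefit.

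The size is unknown. It depends on how many patients follow those growth patterns, how many are caught by other PD routes, how SD duration is counted, and which criteria decide CBR. The rise from 0.09 to between 0.22 and 0.58 is a sensitivity range on assumed shares. It shows that one to three patients matter in a cohort of 25; it does not estimate how many there will be. A much larger inflation could be produced by assuming that early growth usually slows and that only target lesions are read, but the documents supply neither assumption. Nor do they show that CBR is in fact inflated against the control.

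**What to change.** In Appendix 2, define the PD reference as the smallest sum of diameters on study, including the baseline sum, and delete the nadir definition tied to treatment start. Use the same reference for extracranial target lesions, so that PFS follows one rule. Name the same reference in the PD row of Appendix 1, which at present names none.

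The cost is a few words in two appendices, best settled before any CBR is read. The sample size of 25 and the 84% power are unaffected. The downside is that some patients will be called PD earlier than under the literal wording, so CBR and PFS may look slightly less favourable. Section 3 also has the sites use modified RECIST for treatment decisions, so the protocol team should check the amended wording against the sections on treatment after progression.

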Appendix 4: Eastern Cooperative Oncology Group (ECOG) Performance Status Scale

Grade	Description
0	Fully active, able to carry on all pre-disease performance without restriction
1	Restricted in physically strenuous activity but ambulatory and able to carry out work of a light or sedentary nature, e.g., light housework or office work
2	Ambulatory and capable of all self-care but unable to carry out any work activities; up and about >50% of waking hours
3	Capable of only limited self-care, confined to a bed or chair > 50% of waking hours
4	Completely disabled; cannot carry on any self-care; totally confined to bed or chair
5	Dead

Appendix 5: Contraceptive Guidance and Pregnancy Testing

Woman of Childbearing Potential (WOCBP)

A woman is considered fertile following menarche and until becoming post-menopausal unless permanently sterile (see below)

Women in the following categories are not considered WOCBP:

- Pre-menarchal
- Premenopausal female with 1 of the following:
 - Documented hysterectomy
 - Documented bilateral salpingectomy
 - Documented bilateral oophorectomy

Note: Documentation can come from the site personnel's review of the participant's medical records, medical examination, or medical history interview.

- Postmenopausal female
 - A postmenopausal state is defined as no menses for 12 months without an alternative medical cause.
 - A high follicle stimulating hormone (FSH) level in the postmenopausal range may be used to confirm a postmenopausal state in women not using hormonal contraception or hormonal replacement therapy (HRT). However, in the absence of 12 months of amenorrhea, confirmation with two FSH measurements in the postmenopausal range is required.
 - Females on HRT and whose menopausal status is in doubt will be required to use one of the non-hormonal highly effective contraception methods if they wish to continue their HRT during the study. Otherwise, they must discontinue HRT to allow confirmation of postmenopausal status before study enrollment.

Contraception Requirements

Male Participants:

Male participants with female partners of childbearing potential are eligible to participate if they agree to one of the following during the protocol as defined in Section 4.1.1:

- Be abstinent from penile-vaginal intercourse as their usual and preferred lifestyle (abstinent on a long term and persistent basis) and agree to remain abstinent
- Use a male condom plus partner use of a contraceptive method with a failure rate of <1% per year as described in Table 10 when having penile-vaginal intercourse with a woman of childbearing potential who is not currently pregnant.
 - Note: Men with a pregnant or breastfeeding partner must agree to remain abstinent from penile-vaginal intercourse or use a male condom during each episode of penile penetration.

Proprietary Information of MD Anderson

Table 10: Highly Effective Contraceptive Methods That Have Low User Dependency

Highly Effective Methods That Have Low User Dependency Failure rate of <1% per year when used consistently and correctly.

• Progestogen- only contraceptive implant ^{a, b}• Intrauterine hormone-releasing system (IUS) ^b• Intrauterine device (IUD)• Bilateral tubal occlusion

• Vasectomized partner A vasectomized partner is a highly effective contraception method provided that the partner is the sole male sexual partner of the WOCBP and the absence of sperm has been confirmed. If not, an additional highly effective method of contraception should be used.

• Sexual abstinence Sexual abstinence is considered a highly effective method only if defined as refraining from heterosexual intercourse during the entire period of risk associated with the study treatment. The reliability of sexual abstinence needs to be evaluated in relation to the duration of the study and the preferred and usual lifestyle of the participant.

Notes:
 
Use should be consistent with local regulations regarding the use of contraceptive methods for participants of clinical studies.
 
a) If locally required, in accordance with Clinical Trial Facilitation Group (CTFG) guidelines, acceptable contraceptive implants are limited to those which inhibit ovulation.
 
b) If hormonal contraception efficacy is potentially decreased due to interaction with study treatment, condoms must be used in addition to the hormonal contraception during the treatment period and for at least [X days, corresponding to time needed to eliminate study treatment plus 30 days for study treatments with genotoxic potential] after the last dose of study treatment.

Female Participants:

Female participants of childbearing potential are eligible to participate if they agree to use a highly effective method of contraception consistently and correctly as described in Table 11 during the protocol-defined time frame in Section 4.1.1.

Table 11: Highly Effective Contraception Methods

Highly Effective Contraceptive Methods That Are User Dependent ^a Failure rate of <1% per year when used consistently and correctly.

• Combined (estrogen- and progestogen- containing) hormonal contraception ^{b, c}
○ Oral○ Intravaginal○ Transdermal

Proprietary Information of MD Anderson

○ Injectable● Progestogen-only hormonal contraception ^{b, c}
○ Oral○ Injectable

Highly Effective Methods That Have Low User Dependency Failure rate of <1% per year when used consistently and correctly.

● Progestogen- only contraceptive implant ^{b, c}● Intrauterine hormone-releasing system (IUS) ^b● Intrauterine device (IUD)● Bilateral tubal occlusion

● Vasectomized partner A vasectomized partner is a highly effective contraception method provided that the partner is the sole male sexual partner of the WOCBP and the absence of sperm has been confirmed. If not, an additional highly effective method of contraception should be used.

● Sexual abstinence Sexual abstinence is considered a highly effective method only if defined as refraining from heterosexual intercourse during the entire period of risk associated with the study treatment. The reliability of sexual abstinence needs to be evaluated in relation to the duration of the study and the preferred and usual lifestyle of the participant.)

Notes: Use should be consistent with local regulations regarding the use of contraceptive methods for participants of clinical studies.
 
a) Typical use failure rates are lower than perfect-use failure rates (i.e. when used consistently and correctly).
 
b) If hormonal contraception efficacy is potentially decreased due to interaction with study treatment, condoms must be used in addition to the hormonal contraception during the treatment period and for at least [X days, corresponding to time needed to eliminate study treatment plus 30 days for study treatments with genotoxic potential] after the last dose of study treatment .
 
c) If locally required, in accordance with Clinical Trial Facilitation Group (CTFG) guidelines, acceptable hormonal contraceptives are limited to those which inhibit ovulation.

Pregnancy Testing

WOCBP should only be included after a negative highly sensitive urine or serum pregnancy test and in accordance with local requirements. When applicable, this test should be repeated a maximum of 24-hours before the first dose/vaccination.

Following initiation of treatment additional pregnancy testing will be performed at 6-week intervals during the treatment period and at 120 days after the last dose of study treatment and as required locally.

Pregnancy testing will be performed whenever an expected menstrual cycle is missed or when pregnancy is otherwise suspected.

Proprietary Information of MD Anderson

